The investigator may schedule visits (unplanned visits) in addition to those listed on the schedule of activities, in order to conduct evaluations or assessments required to protect the well-being of the subject.

Property of GSK Consumer Healthcare

Confidential

May not be used, divulged, published or otherwise disclosed
without the consent of GSK

Template Version Effective: 22-Jun-2017

Page 10 of 61

Document Name	090032d580fbc076protocol.pdf				
Type	Version			Document Identifier	Effective Date
eldo clinicaldbc	0.0	090032d580fbc076protocol		090032d580fbc076	24-Aug-2017 09:06:22
Reason For Issue	Auto Issue				

Potassium Nitrate / Sodium Fluoride

208078

Final 1.0 Clinical Protocol

Table 13-1 Schedule of Activities

Procedure/Assessment	Screening	Visit 1	Study Period				End of Treatment	
	Visit 2 Baseline (MLSI) Day 1		Visit 3 Baseline (TPI) Day 2	Visit 4 Week 2 Day 15 ± 1 days	Visit 5 Week 4 Day 29 ± 2 days	Visit 6 Week 8 Day 57 ± 3 days	Visit 7 Week 8 Day 58 ± 3 days	
Informed Consent		X						
Demographics, Ethnicity		X						
Medical History and Current Medication		X						
OST Examination		X		X	X	X	X	X
OHT Examination		X	X					
Visual MLSI Stain Assessment of the 12 Anterior Teeth		X						
Review Inclusion / Exclusion Criteria ¹		X	X					
Concomitant Medication			X	X	X	X	X	X
Eligibility		X	X					
Instruct Subjects on the Lifestyle Guidelines and Concomitant Treatment(s) Sections of the Protocol		X						
Brush Anterior Teeth for 30 Seconds with Tap Water Prior to Stain Assessment			X	X	X	X	X	

Property of GSK Consumer Healthcare

Confidential

May not be used, divulged, published or otherwise disclosed
without the consent of GSK

Template Version Effective: 22-Jun-2017

Page 11 of 61

Document Name	090032d580fbc070protocol.pdf				
Type	Version			Document Identifier	Effective Date
eldo clinical@bc	0.0	090032d580fbc070protocol		090032d580fbc070protocol	24-Aug-2017 09:06:22
Reason For Issue	Auto Issue				

Potassium Nitrate / Sodium Fluoride

208078

Final 1.0 Clinical Protocol

Procedure/Assessment	Screening	Study Period				End of Treatment	
	Visit 1	Visit 2 Baseline (MLSI) Day 1	Visit 3 Baseline (TPI) Day 2	Visit 4 Week 2 Day 15 ± 1 days	Visit 5 Week 4 Day 29 ± 2 days	Visit 6 Week 8 Day 57 ± 3 days	Visit 7 Week 8 Day 58 ± 3 days
Full MLSI Stain Assessment of the Anterior Teeth ²		X		X	X	X	
Repeat MLSI Stain Assessment ³		X		X	X	X	
Selection of 4 Assessment Teeth		X					
Stratification		X					
Unsupervised Brushing on Site ⁴		X	X				X
Plaque Disclosing Followed by Pre-brushing TPI Assessment ⁵			X				X
Randomization and Dispense Study Dentifrice, Timer, Toothbrush and Diary/Instructions Card			X				
Supervised Brushing on Site ⁶			X	X	X	X	X
Plaque Disclosing Followed by Post-brushing TPI Assessment ⁴			X				X
Repeat TPI Assessment ³			X				X
Adverse Events ⁷		X	X	X	X	X	X
Incidents ⁸		X	X	X	X	X	X
Subjects Return Dentifrice, Toothbrush and Diary Card				X	X	X	X
Subject Adherence and Continuance ⁹			X	X	X	X	X
Diary Compliance Check				X	X	X	X

GlaxoSmithKline Consumer Healthcare Confidential

Template Version Effective: 22-Jun-2017

Page 12 of 61

Document Name	090032d580fbc070protocol.pdf				
Type	Version			Document Identifier	Effective Date
elido clinical@bc	0.0; 090032d580fbc070; Current			090032d580fbc070	24-Aug-2017 09:06:22
Reason For Issue	Auto Issue				

Potassium Nitrate / Sodium Fluoride

208078

Final 1.0 Clinical Protocol

Procedure/Assessment	Screening	Study Period					End of Treatment	
		Visit 1	Visit 2 Baseline (MLSI) Day 1	Visit 3 Baseline (TPI) Day 2	Visit 4 Week 2 Day 15 ± 1 days	Visit 5 Week 4 Day 29 ± 2 days	Visit 6 Week 8 Day 57 ± 3 days	Visit 7 Week 8 Day 58 ± 3 days
Study Conclusion								X

Abbreviations: OST= Oral Soft Tissue; OHT = Oral Hard Tissue; MLSI = Macpherson Modification of the Lobene Stain Index; TPI = Turesky Plaque Index.

¹ At Visit 2 a review of Inclusion Criteria 10 and Exclusion Criteria 12.b and e will be conducted, and at Visit 3 a review of Inclusion Criteria 11 will be conducted.

² At Visit 2 a full MLSI assessment of the 12 anterior teeth will be conducted, at Visits 4, 5 and 6 a full MLSI assessment of the 4 assessment teeth will be conducted

³ Five subjects will be randomly selected for repeat MLSI and TPI examinations across each assessment window (a total of 20 repeat MLSI and 10 repeat TPI examinations over the duration of the study).

⁴ This will be with a standard fluoride dentifrice administered by the site. Once all efficacy assessments have been completed, subjects will be allowed to brush unsupervised prior to leaving the clinical study site.

⁵ Two disclosing rinses with the plaque disclosing solution will be conducted, one prior to the pre-brushing TPI assessment and one prior to the post-brushing TPI assessment.

⁶ The supervised brushing at Visits 4, 5, and 6 will be conducted following the MLSI stain assessments.

⁷ Any serious adverse event assessed as related to study participation that occurs subsequent to the signing of informed consent and any adverse event subsequent to brushing with the standard fluoride dentifrice at Visit 2. For those subjects that don't brush with the standard fluoride dentifrice at Visit 2 adverse events will be collected from first use of the plaque disclosure solution at Visit 3.

⁸ Incidents will be collected from first use of the tooth brush, prior to stain assessment.

⁹ Time of each brushing occasion in addition to missed/additional brushings will be captured in the subject diary.

GlaxoSmithKline Consumer Healthcare Confidential

Template Version Effective: 22-Jun-2017

Page 13 of 61

Document Name	003208076tprotocol.pdf	Document Identifier	Effective Date
Type	Version		
eldo_clinicalelbc	0.0. DIFFERENT MESSAGING CURRENT	1090032d580fb904c	14-Aug-2017 09:06:22

Potassium Nitrate / Sodium Fluoride

208078

Final 1.0 Clinical Protocol

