10. In the opinion of the investigator, **at Visit 2**, subjects must have a sufficient level of extrinsic dental stain (in the opinion of the examiner) on the facial surfaces of the scorable anterior (maxillary and mandibular) teeth.
11. **At Visit 3**, a minimum overall pre-brushing plaque score (TPI) of ≥ 2.0 .

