4.4 Lifestyle Guidelines

Eligible subjects will continue to use their current dentifrice (according to their normal habit) between the screening and baseline visits, and will return to the site for the baseline visit a minimum of 24 hours, or up to a maximum of 2 weeks after screening.

Document Name	0032080761pcotol.pdf	Document Identifier	Effective Date
Type	Version		
eldo_clinicalelbc	0.0. DIFFERENT MESSAGING CURRENT	1090032d580f8944c	14-Aug-2017 09:06:22

Potassium Nitrate / Sodium Fluoride

208078

Final 1.0 Clinical Protocol

Following the supervised brushing with the standard fluoride dentifrice at the baseline (MLSI) visit up until completion of the study, subjects must only use the study products provided to them. Subjects will abstain from chewing gum and will not use any dental products, including home remedies for tooth whitening, other than the study products provided for the duration of the study. Subjects will be permitted to use non-antimicrobial dental floss for the removal of impacted food only.

On MLSI assessment days (Visits 2, 4, 5 and 6) subjects will attend the study site having refrained from all oral hygiene procedures for at least 6 hours.

On TPI assessment days (Visits 3 and 7) subjects will attend the study site having refrained from all oral hygiene procedures for 24 hours (+6, or -2 hours; including not brushing the evening before).

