- Review Inclusion and Exclusion criteria. Pregnancy status will be confirmed verbally by the subject.
- Confirmation of subject eligibility.
- To prepare for study participation, instruct subjects on the use of the [Lifestyle Guidelines](#) and [Concomitant Treatment\(s\)](#) sections of the protocol.

6.1.2 Baseline MLSI Visit (Day 1) - Visit 2

Subjects will be admitted to the clinical site at least 24 hours following the Screening visit. Subjects will attend the study site having refrained from all oral hygiene procedures for at least 6 hours, and from eating and drinking for at least 2 hours (with the exception of water), prior to their scheduled visit.

The following procedures will be completed in the following order (where possible), and recorded in the CRF:

- Review changes in the subject's medical history including concomitant medication since Screening.
- Review of Inclusion Criteria 10, and Exclusion Criteria 12.b and e.
- Full OHT and OST examinations conducted by a medically qualified examiner. Record any changes since the Screening visit in the CRF.
- Confirm subject eligibility and continuance.
- Supervised brushing of the anterior teeth for 30 seconds using a wetted toothbrush, followed by flossing.
- Full MLSI stain assessment of the facial (maxillary and mandibular) teeth conducted by a qualified dental examiner.

GlaxoSmithKline Consumer Healthcare Confidential

Template Version Effective: 22-Jun-2017

Page 31 of 61

Document Name	003270B076tpctocol.pdf	Document Identifier	Effective Date
Type	Version		
eldo_clinicalelbc	0.0. DIFFERENT MESSAGING CURRENT	1090032d580fb904bc	14-Aug-2017 09:06:22

Potassium Nitrate / Sodium Fluoride

208078

Final 1.0 Clinical Protocol

- 4 eligible assessment teeth selected by a qualified dental examiner.
- Repeat full MLSI stain assessment of the 4 assessment teeth for selected subjects.
- Stratification (based on total MLSI score of the 4 facial surfaces of the 4 eligible assessment teeth).
- Unsupervised brushing with standard fluoride dentifrice.
- AEs and incidents. Assess symptoms by spontaneous reporting of adverse events and by asking the subjects to respond to a non-leading question such as “How do you feel?”

6.1.3 Baseline TPI Visit (Day 2) - Visit 3

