Subjects will be admitted to the clinical site 24 hours (+6, or -2 hours; including not brushing the evening before) after Visit 2, and will be requested to refrain from eating and drinking for at least 2 hours (with the exception of water), prior to their scheduled visit.

Prior to randomization the following procedures/assessments will be completed in the following order (where possible), and recorded in the CRF:

- Review changes in the subject's medical history including concomitant medication since the previous visit.
- Review of Inclusion Criteria 11.
- Confirmation of subject adherence and continuance. Full OST examination conducted by a medically qualified examiner.
- Subjects disclose plaque by rinsing with plaque disclosure solution.
- Pre-brushing full mouth TPI assessment of all gradable teeth, conducted by a qualified dental examiner.
- Randomization.

Following randomization, the following procedures/assessments will be completed in the following order (where possible), and recorded in the CRF:

- Dispense study dentifrice, toothbrush and diary/ instructions card.
- Supervised brushing with subject's allocated dentifrice. The time of brushing will be entered in the CRF.
- Subjects disclose plaque for a second time by rinsing with plaque disclosure solution.
- Post-brushing full mouth TPI assessment of all gradable teeth, conducted by a qualified dental examiner.
- Repeat TPI assessment conducted by a qualified dental examiner, for selected subjects.
- Post assessment brushing with standard fluoride dentifrice and toothbrush (if requested by the subject).

Document Name	003270B076tprotocol.pdf	Document Identifier	Effective Date
Type	Version		
eldo_clinicalellbc	0.0. DIFFERENT MESSER Revision CURRENT	1090032d580f8904c	14-Aug-2017 09:06:22

Potassium Nitrate / Sodium Fluoride

208078

Final 1.0 Clinical Protocol

- AEs and incidents captured. Assess symptoms by spontaneous reporting of adverse events and by asking the subjects to respond to a non-leading question such as “How do you feel?”

6.1.4 Day 15 (MLSI) - Visit 4

Subjects will be admitted to the clinical site having refrained from all oral hygiene procedures for at least 6 hours, and from eating and drinking for at least 2 hours (with the exception of water), prior to their scheduled visit.

The following procedures/assessments will be completed in the following order (where possible), and recorded in the CRF:

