- Full MLSI stain assessment of the 4 assessment teeth by a qualified dental examiner.
- Repeat full MLSI stain assessment of the 4 assessment teeth for selected subjects.
- Supervised brushing with subject's allocated dentifrice for 60 seconds.
- AEs and incidents captured. Assess symptoms by spontaneous reporting of adverse events and by asking the subjects to respond to a non-leading question such as "How do you feel?"

6.1.6 Day 57 (MLSI) - Visit 6

Subjects will be admitted to the clinical site having refrained from all oral hygiene procedures for at least 6 hours, and from eating and drinking for at least 2 hours (with the exception of water), prior to their scheduled visit.

The following procedures/assessments will be completed in the following order and recorded in the CRF:

- Subjects return study dentifrice, toothbrush, and diary card to the clinical site.
- Review changes in the subject's medical history including concomitant medication since the previous visit.
- Review of completed diary to confirm timing of each brushing occasion in addition to missed/additional brushings.
- AEs and incidents captured. Assess symptoms by spontaneous reporting of adverse events and by asking the subjects to respond to a non-leading question such as "How do you feel?"
- Confirmation of subject adherence and continuance.
- Full OST examination conducted by a medically qualified examiner.
- Supervised brushing of the anterior teeth for 30 seconds using a wetted toothbrush, followed by flossing.
- Full MLSI stain assessment of the 4 assessment teeth by a qualified dental examiner.
- Repeat full MLSI stain assessment of the 4 assessment teeth for selected subjects.
- Supervised brushing with subject's allocated dentifrice for 60 seconds.

Document Name	003270B076tpotocol.pdf	Document Identifier	Effective Date
Type	Version		
eldo_chincontrolledbc	0.0. DIFFERENT MESSAGING CURRENT	1090032d580fb904bc	14-Aug-2017 09:06:22

Potassium Nitrate / Sodium Fluoride

208078

Final 1.0 Clinical Protocol

- AEs and incidents captured. Assess symptoms by spontaneous reporting of adverse events and by asking the subjects to respond to a non-leading question such as “How do you feel?”

6.1.7 Day 58 (TPI) - Visit 7

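### The protocol is inconsistent on whether every subject brushes at the end of Visit 2, so plaque on the non-anterior teeth at Visit 3 may be 22 to 30 hours old or at least 28 to 36 hours old

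*Protocol*

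**What the plan says.** The protocol describes the same Visit 2 step in several ways:

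- **Section 6.1.2** lists "Unsupervised brushing with standard fluoride dentifrice" among the visit's procedures with no condition attached. The corresponding items in 6.1.3 (Visit 3) and 6.1.7 (Visit 7) are made dependent on the subject asking for it. The schedule of activities ticks the row at Visit 2.
- **Section 4.4** presupposes the step but calls it supervised: "Following the supervised brushing with the standard fluoride dentifrice at the baseline (MLSI) visit" is the point from which only study products may be used.
- **Schedule footnote 4**, attached to that row for Visits 2, 3 and 7, makes it a permission: "Once all efficacy assessments have been completed, subjects will be allowed to brush unsupervised prior to leaving the clinical study site".
- **Schedule footnote 7** sets a different start for adverse event collection: "For those subjects that don't brush with the standard fluoride dentifrice at Visit 2". Section 8.2.1 repeats the provision.

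Two timing rules apply to Visit 3. Section 6.1.3 counts from the previous visit: "Subjects will be admitted to the clinical site 24 hours (+6, or -2 hours; including not brushing the evening before) after Visit 2". Section 4.4 counts from the last oral hygiene, with subjects attending plaque visits "having refrained from all oral hygiene procedures for 24 hours (+6, or -2 hours". Before Visit 2 itself, 4.4 asks for at least 6 hours without oral hygiene and sets no maximum.

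The Visit 3 pre-brushing score is the subject of criterion 11, "a minimum overall pre-brushing plaque score (TPI) of" 2.0 or more. It is also the plaque baseline (SAP 3.1) and the ANCOVA covariate (SAP 4.6.1.2). At Week 8 the matching step, in 6.1.6, is a supervised brushing with the subject's "allocated dentifrice for 60 seconds", listed for everyone.

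**The concern.** The Visit 2 brushing is what starts the 24-hour plaque build-up. The only other cleaning planned at that visit is a 30-second brushing of the anterior teeth with a wet brush, followed by flossing, whereas TPI is scored on all gradable teeth. If some subjects brush and others do not, the Visit 3 score describes plaque of different ages.

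Three things depend on that score. Criterion 11 could be met partly because a brushing was skipped. Baseline TPI would carry avoidable variability. Where plaque grows with time, a subject who skipped starts Week 8 comparisons from older plaque than is scored at Visit 7, so part of the fall from baseline would be procedural. SAP Table 14.2.6.2 reports adjusted mean changes with confidence intervals and p-values within each arm, so that fall will be read.

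The planned data could not repair this. Section 6.1.2 asks for no time of brushing at Visit 2, although 6.1.3 has the Visit 3 brushing time entered in the CRF, and the diary is dispensed only at Visit 3.

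**Working it through.** **Inputs**

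- *g*, interval from Visit 2 to Visit 3: 24 h, +6 or −2 (6.1.3), so 22 to 30 h.
- *a*, time without oral hygiene before Visit 2: at least 6 h, no maximum (4.4, 6.1.2).
- Abstention allowed before a plaque visit: 24 h, +6 or −2 (4.4), so at most 30 h.
- The length of Visit 2 is ignored. The dentifrice brushing is taken to be full-mouth, as no text restricts it.

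**Subject who brushes at the end of Visit 2.** Plaque age = *g* = 22, 24 or 30 h (low, nominal, high). This reproduces the plan's own interval, and 4.4 and 6.1.3 agree.

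**Subject who does not.** Time since the last full-mouth brushing = *a* + *g*. At the 6 h minimum:

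- low: 6 + 22 = 28 h
- nominal: 6 + 24 = 30 h
- high: 6 + 30 = 36 h

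These are lower bounds, because *a* has no ceiling. The documents do not give actual values of *a*. For assumed values at the nominal interval:

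| Assumed *a* | *a* + 24 h |
|---|---|
| 8 h | 32 h |
| 11 h | 35 h |
| 14 h | 38 h |

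**Can a non-brusher satisfy both timing rules?** This needs *a* + *g* ≤ 30. With *g* ≥ 22, *a* can be at most 30 − 22 = 8 h. With *a* ≥ 6, *g* can be at most 30 − 6 = 24 h. So both rules hold only if the pre-visit abstention is 6 to 8 h, the interval is 22 to 24 h, and the two sum to no more than 30 h. At exactly the nominal interval, the 6 h minimum already reaches the 30 h limit. Anything longer exceeds it while remaining in window under 6.1.3.

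**How much of the score is affected?** Criterion 7 requires at least 20 teeth including the 12 anterior, and wisdom teeth are not scored, so at most 28 are. The anterior teeth, brushed with water in everyone, are therefore 12/28 = 43% to 12/20 = 60% of those scored. The extra age applies mainly to the rest.

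**Week 8.** Everyone brushes at Visit 6, so plaque at Visit 7 is 22 to 30 h old. This reads 6.1.7 as counting from Visit 6; it prints Visit 2, but Section 1.2.2 puts stain and plaque assessments one day apart. For the same interval, a subject who skipped at Visit 2 has a baseline older by *a*, at least 6 h.

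**The case against.** The best defence is that the conflict is mostly wording. Section 6.1.2 lists the step unconditionally, the schedule ticks it, and Section 5.4 supplies dentifrice for brushing after the stain baseline. Footnote 4 serves three visits, so its permissive tone may belong to the two where brushing is on request. Footnote 7 and 8.2.1 fix when adverse event collection starts and do not say that skipping is acceptable. Section 4.4 also limits abstention to 30 h for everyone, so a subject beyond that is a deviation, and adherence is confirmed at Visit 3 before plaque is disclosed.

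The probable intent is a fair inference, but the text still provides for non-brushers, and a site could follow either reading. The 30 h limit does not resolve it: most non-brushers cannot meet 4.4 and 6.1.3 together, and with no recorded time nobody can tell who did. If the water brushing and flossing at Visit 2 count as oral hygiene, a non-brusher complies with 4.4, but then that limit does not control the age of plaque on the posterior teeth.

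The limits on consequence stand in full. The choice to brush comes before randomization and baseline TPI is a covariate. The plaque objectives rank products and are exploratory. The single-use endpoint is a change within one visit. Part of the mouth is cleaned in everyone.

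**Conclusion.** The contradiction is real and should be corrected, with modest consequences. A subject who skips the Visit 2 brushing has at least 28 to 36 h since the last full-mouth brushing when plaque is scored, against 22 to 30 h for one who brushes. This affects comparability at criterion 11, the variability of baseline TPI, and within-arm change to Week 8. The last of these also assumes that plaque scores rise over those extra hours. The documents give no rate, so the effect cannot be put in TPI units, and they do not say what share of subjects would skip.

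Three stronger readings are not supported:

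- *Plaque at Visit 3 would be about 35 h old, or 46% older than at Week 8* (35/24 = 1.46). That needs an assumed 11 h of abstention before Visit 2. It is one example among many and describes the non-anterior teeth rather than the whole mouth.
- *The comparison between products is biased.* The choice precedes allocation, so no systematic difference between arms is expected.
- *The main result is at risk.* The baseline stain score is taken before this brushing, so the primary and secondary MLSI endpoints are unaffected.

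**What to change.** 1. Reconcile the schedule row, footnotes 4 and 7, and Sections 4.4, 6.1.2 and 8.2.1 to one rule on the Visit 2 brushing. It should settle both whether the step is done and whether it is supervised, apply to all subjects, and give plaque build-up before Visit 3 the same starting point as before Visit 7. Visit 2 needs its own footnote, separate from Visits 3 and 7.
2. Record in the CRF whether each subject brushed at Visit 2 and at what clock time.
3. In 6.1.3, count the 24 h (+6 or −2) from that recorded brushing, so that it agrees with 4.4. Correct the visit reference in 6.1.7 at the same time.
4. Treat subjects outside the interval as deviations at the blinded data review. SAP Amendment 1, Section 3.3, accepts all data and calls visit-window deviations minor, so it should say that this interval is reviewed. Barring the criterion 11 score outside the interval is not recommended: it would add an eligibility gate, and Section 4.5 does not allow screen failures to be re-screened.

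The cost is protocol wording, one CRF field and about one minute per subject. Dentifrice, brush and staff are already at the visit.

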1 INTRODUCTION

Dentifrices are often recommended by dentists to help remove oral debris and dental plaque [Pader, 2012]. Dental plaque is a soft, sticky, colourless deposit of bacteria which collects on the teeth and along the gingival margin. Bacterial by-products from dental plaque can affect the health of the gingiva by causing inflammation of the gingival tissue [Davies, 2008]. Gingivitis and periodontal disease can develop when dental plaque accumulates above levels compatible with oral health [Marsh, 1992]. Mechanical plaque removal by toothbrushing is the most effective way to reduce plaque, and whilst the proper use of a toothbrush is effective in removing dental plaque [Pader, 2012], it is understood that the general population will brush using an inadequate technique, and for significantly less time than the recommended and accepted 2 minutes [Gallagher, 2009]. Clinical data support that brushing with a dentifrice that has been formulated with chemical and/or abrasive agents to help remove plaque, will facilitate, or enhance plaque removal efficacy [Davies, 2008; Parkinson, 2014; Ayad, 2015; Parkinson 2015; Feng, 2016].

The etiology of stain is multiple but is widely agreed to result from discolouration of plaque and pellicle on the surface of the tooth, with the main site for extrinsic stain build up generally accepted as the acquired salivary tooth pellicle [Shellis, 2005]. Therefore, plaque removal is considered to be an important feature in the prevention of stain build-up and thus careful selection of an appropriate abrasive and/or chemotherapeutic agents should be an important consideration when formulating dentifrices designed to enhance plaque removal.

The ability of a dentifrice to help control dental stain is also considered to be a key characteristic [Pader, 2012]. Extrinsic dental stain removal is typically achieved by the inclusion of dental grade abrasives such as silicas and chemical cleaning agents such as polyphosphates. A range of parameters have been shown *in vitro* to affect the stain removal and wear properties of abrasives including particle hardness, shape, size, distribution, and concentration [Joiner, 2010; Schemehorn, 2011]. Dental grade abrasive silicas are often relatively hard abrasives that are typically formulated in anti-sensitivity dentifrices within the range of 6-16% and, while effective at cleaning, often lend high abrasivity to dentifrices.

CCI

It is currently hypothesized that the greater volume of smaller spherical silica particles offer a higher surface area of cleaning particles, and whilst further *in vitro* work should be conducted to elucidate the mode of action of spherical silica, it is prudent to explore if these results can also be replicated clinically.

Property of GSK Consumer Healthcare

Confidential

May not be used, divulged, published or otherwise disclosed
without the consent of GSK

Template Version Effective: 22-Jun-2017

Page 14 of 61

Document Name	093270B076tpcofocal.pdf	Document Identifier	Effective Date
Type	Version		
eldo_clinicalelbc	0.0 DIFFERENT MESSER Revision CURRENT	1090032d580fb994c	14-Aug-2017 09:06:22

[figure not shown]
Potassium Nitrate / Sodium Fluoride

208078

Final 1.0 Clinical Protocol

Polyphosphates, such as sodium tripolyphosphate (STP), can also be included as chemical cleaning compounds, either on their own or to supplement the physical stain removal offered by dental abrasives. Polyphosphates act as chelating ingredients and have been shown to bind strongly to the tooth surface, reducing the force of adhesion of adsorbed proteins [Shellis, 2005] and facilitating stain removal during toothbrushing. In addition, they have been shown to desorb salivary proteins from enamel, and inhibit protein adsorption [Rykke, 1988; Rykke 1990], thereby helping to control stain build up.

CCI

Given that it is of importance that a dentifrice should clean and control extrinsic dental stain whilst minimising its abrasive effect [Schemehorn, 2011], particularly for people with tooth sensitivity where the softer dentin is exposed [Pickles, 2006] reduced abrasivity is considered to be advantageous in anti-sensitivity dentifrices.

This clinical study will compare an experimental low abrasivity 0.5% spherical silica dentifrice and a marketed low abrasivity 6% standard abrasive dentifrice, and an experimental moderate abrasivity 1% spherical silica / 5% STP dentifrice and a marketed high abrasivity 16% standard abrasive silica / 5% STP dentifrice. The main aims of this study are to determine whether spherical silica can achieve similar or greater extrinsic dental stain and plaque removal, in comparison to dentifrices containing higher concentrations of standard abrasive silica, and how the addition of 5% STP enhances cleaning capability. This study has not been designed to demonstrate the specific contribution that spherical silica or STP, are having on the overall reduction of stain and plaque.

